4.5 Vaccine and immunization

The study vaccine will be Gardasil®9 (Merck Canada, Inc), a recombinant, 9-valent vaccine that protects against HPV. A single manufacturing lot of vaccine will be obtained for this study, if possible.

4.5.1 Storage

Vaccine should be stored refrigerated at 2°-8°C, avoiding freezing. Vaccine storage temperature will be monitored and recorded daily.

4.5.2 Immunization

Study vaccine must be injected intramuscularly, with the deltoid muscle of the non-dominant arm being the preferred site. Immunizers will use 25 gauge needles, 1 inch in length, with built-in safety caps. Sharps will be disposed of in appropriate containers.

4.6 Serologic Testing (PBMC details in appendix 1)

4.6.1 Sample collection and handling of specimens

Blood samples (35 ml) for B cell testing will be collected by venipuncture in 4 yellow caps (ACD BD Vacutainer tubes). Each tube of blood will be clearly labeled with PID and visit number, secondary identifier (SID) and date and time of collection. Samples will be collected from all participants at visits 1 to 3. The

volume of blood to be collected at each visit is up to 45 ml. The minimum sample volume is 20 ml. Each tube should be gently inverted 8 times to mix blood and anticoagulant. The blood sample should be held at room temperature until processed, which should take place within 4 hours of the blood draw. Processing should occur between 30 minutes and 4 hours post draw. The samples will be centrifuged to separate the plasma from the cells. Plasma should be stored in numerical order (by PID) and in sequence per participant in a vertical position at -20 °C to -80 °C until shipped to the designated laboratory. An accurate list of serum samples will be maintained.

Blood samples (10 ml) for serology testing will be collected by venipuncture in clotted SST Vacutainer tubes. Clotted specimens must be transferred to cold storage (2 °C - 8 °C) after clotting has fully completed (30-60 minutes). Cold storage must be maintained after 60 minutes until serum separation. Clotted specimens will be separated using manufacturer specifications within 24 hours of collection. Sera must be aseptically transferred to standard, labeled cryovial tubes and stored at -20 °C to -80° C.

4.6.2 Processing, storage and transport of specimens

PBMC should be labeled by PID and in sequence per participant. An accurate list of PBMC samples will be maintained. PBMC will be processed by Ficoll Paqe density gradient centrifugation, stored and shipped as per the lab manual of Appendix 1. Both PBMC and plasma samples will be stored at -20 °C to -80° C and shipped to the [name] lab in Seattle, WA on dry ice. Serum samples will be stored at -20 °C to -80° C and shipped to Merck Canada Inc. research facility for antibody response testing.

4.6.3. Immune response testing

PBMC will be enriched for B cells through negative selection with beads. The HPV specific Bmem express a cell surface BCR that binds to Alexafluor labeled HPV pseudovirus. That together with phenotypic markers allows us to isolate HPV-specific Bmem by FACS. Variable regions of the heavy and light chains will be cloned from singly sorted cells to allow us to assign V gene usage and to determine the extent of somatic hypermutation. The sequences from the leader region to the constant region are cloned into antibody vectors, expressed in 293 cells and antibodies are purified and tested for their ability to bind to HPV L1 proteins and to neutralize pseudoviruses. In addition to sequencing antibody genes from single cells next generation sequencing (NGS) will be used to sequence bulk populations of Bmem and plasmablasts to more extensively cover the repertoire. Because plasmablasts do not express a BCR, HPV specific PBs cannot be isolated but it has been estimated that approximately 70% of PBs are antigen specific within a week following vaccination.

Merck will perform serology testing for antibodies to HPV 6, 11, 16 and 18.

4.7 Vaccine safety

4.7.1 Immediate post-vaccination observation for anaphylaxis

Participants will be observed for at least 15 minutes after vaccination for any signs or symptoms of anaphylaxis or other distress. Study staff will be equipped to assess such changes and to administer appropriate initial medication.

4.7.2 Reporting of adverse events following immunization

Surveillance for provincially reportable adverse events following immunization (AEFI) will conform to recommended practices in British Columbia. At Visits 2 and 3 participants will be asked about any AEFI of concern to them, especially if medical consultation was required. Adverse events that qualify for reporting will be reported to British Columbia Centre for Disease Control using the provincial AEFI reporting form. Participants will be advised when reporting is done on their behalf by study staff.

4.7.3 Reporting of serious adverse events (SAEs)

Participants will be asked to advise the investigator as soon as possible of any Serious Adverse Event that occurs while enrolled in the study. Details of the SAE are to be explored in sufficient detail to enable the investigator to assess the likelihood that it was caused by the vaccination. SAEs will be identified on the adverse event section of the e-CRF and reported on the paper SAE form. All SAEs should be reported, including those that are considered unrelated to study vaccination. The study site will report all SAEs to the REB as is applicable per REB guidance notes.

An SAE is any untoward medical occurrence that:

- results in death
- is life threatening
- requires inpatient hospitalization
- results in significant incapacity or disability (significant disruption in conducting normal life functions)
- is a congenital anomaly/birth defect in the offspring of a study subject

4.8 Ongoing Eligibility

4.8.1 Contraindications to subsequent blood draws

A blood sample will not be drawn if in the interim:

- Blood or blood-derived product administration was required
- Additional dose of any HPV vaccine was administered
- Immune compromise developed as a result of illness or medication
- New bleeding disorder developed that contraindicates blood collection

4.8.2 Deviations

Participants may be retained in the study in the following circumstances but will be flagged as having deviated from the protocol:

- Any visits outside of window
- If the volume of blood collected is insufficient to obtain a lab result
- No blood obtained at Visit 2 (Day 7)

4.8.3 Withdrawals

Study staff will attempt to contact participants who do not return for a scheduled visit, making at least 4 attempts by various means of communication. Each attempt should be documented in the source document/study file. Due diligence must be made to ascertain the well-being of participants who were immunized.

Withdrawals will be documented, including date of withdrawal and reason if known. All data obtained before withdrawal may be included in the study analysis.

Participants should be withdrawn from the study in the following circumstances

- Withdrawal of consent to participate
- Unresolved condition beginning after enrollment that renders participant ineligible and is unlikely to resolve (e.g. immune compromise, bleeding disorder)
- Missing blood at Visit 3 (Day 30)

4.9 Non-study vaccines

For the purposes of post vaccine adverse event collection, other routine vaccinations should not be administered concurrently with the HPV9 vaccination. In addition, leading up to study enrollment, participants should not have received a live vaccine within 28 days or an inactive vaccine within 14 days of Visit 1.

5.0 DATA COLLECTION

Data will be collected on source documents (paper) and transferred as applicable to an electronic case report form (e-CRF). Data entry will be completed by trained center personnel shortly after each scheduled encounter with participants. The following data elements will be collected:

Demographics: birth month and year.

Baseline Health History: height, weight, and any health conditions requiring ongoing medical follow-up or care, any currently prescribed medications taken over the study.

HPV immunization history: date (month and year) of each dose is required

Protocol compliance: consent date and time, visit dates; immunization details (protocol adherence regarding administration including participant temperature prior to immunization, cold chain maintenance, date, time); blood sample details (protocol adherence regarding cold chain, volume obtained, dates and times); occurrence of reportable or serious adverse events, any deviations; any withdrawals, with specific reason.

5.1 Data entry

Data entry will be performed by trained staff of the VEC. To minimize transcription errors, the study database will contain numerous pre-programmed edit checks and prompts to enter missing data.

5.2 Data security measures

Data will be entered into the database platform, Dacima Clinical Suite. Dacima Clinical Suite is an encrypted data management platform with strict user access settings and is hosted in a secure data facility in Montreal. The facility has 24 hour security, internal and external back-up measures and disaster recovery plans in place.

5.3 Confidentiality protection

Source documents containing names, addresses and other contact information of participants will be stored in individual folders, identified by the assigned PID number. These documents are stored in lockable filing cabinets in a secure research facility, with controlled access, limited to authorized staff and investigators. No personal identifiers will appear in the CRF or on serum and PBMC tubes, laboratory requisitions or reports. No personal identifiers will appear in any summary or report of the study data.

In keeping with legal obligations, investigators will report any reportable AEFIs to the local Health Department using the prescribed provincial report form. This form requires inclusion of personal identifiers to enable public health to add this information to the participant's central immunization record and to follow-up the event if warranted by its nature or severity.

All VEC staff and investigators participating in this study will have completed PHSA's Confidentiality training module and have a completion certificate on file.

6.0 DATA ANALYSIS PLAN

6.1 Demographics and participation analysis

Frequency analysis will be conducted on demographic data, baseline health history and immunization history. De-identified data will be provided to the Seattle laboratory.

6.2 Immune response analyses

HPV type specific Bmem will be obtained as described above; their number and frequency will be analyzed at the third visit. The difference between the visit 1 and visit 3 Bmem will be obtained for all subjects. The extent of somatic hypermutation will be determined by comparing the nucleotide sequences of the heavy and light chain variable region sequences of each antibody cloned in this study to germ line sequences of these genes in public databases. These data bases will allow us to assign V, D and J gene usage.

Plasmablast numbers and frequencies will be obtained by FACS analysis of the week one samples.

Human monoclonal antibodies will be cloned and expressed from the Bmem at the first and third visit samples. The purified antibodies will be tested in binding assays to the L1 proteins of numerous HPV types to determine their type-specificity. The antibodies will be tested in pseudovirus-based neutralization assays to any type to which they bind to determine the IC₅₀.

Mean antibody levels and seropositivity prior to and after the booster dose of vaccine for HPV types 16, 18, 6, and 11 and the geometric mean titres of antibody levels against HPV 16, 18, 6, and 11 will

be compared between cohorts using two-sample t-test. To allow GMT calculation, samples with undetectable anti-HPV will be assigned half of the lowest detectable value.

All measurements will be compared between the two dose vs. three dose girls as well as the 3 dose women.

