2.0 OBJECTIVES

Primary objective:

- To compare the B memory and plasmablast populations between girls and young women that received either a primary 2 or 3 dose series, who are then challenged with a subsequent dose after 120 months.

Secondary objectives:

- To compare the extent of somatic hypermutation and the variable gene usage between girls that received either a primary 2 or 3 dose series.
- To compare the serum antibody responses to HPV 6, 11, 16 & 18 at month 120 in females that received either a primary 2 or 3 dose series, who are then challenged with a subsequent dose.

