3.0 STUDY DESIGN AND PARTICIPANT OVERVIEW

This is a single center, interventional study to evaluate long term memory response to HPV 6, 11, 16 & 18. Memory response will be assessed by measuring seroprotection 8-10 years post Q-HPV vaccination and to challenge with a booster dose of HPV9 vaccine (Gardasil® 9, Merck Canada, Inc.) years after the original exposure to measure the long-lasting anamnestic response. This is a 3 arm study with 6 girls per group:

Group 1: girls who received 2 doses of Q-HPV vaccine at 0, 6 month schedule 8-10 years ago when they were between 9-13 years of age at the time of the first dose.

Group 2: girls who received 3 doses of Q-HPV vaccine at 0, 2, 6 month schedule 8-10 years ago when they were between 9-13 years of age at the time of the first dose.

Group 3: young women who received 3 doses of Q-HPV vaccine at 0, 2, 6 month schedule 8-10 years ago when they were between 16-26 years of age at the time of the first dose.

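### Plasmablasts are counted only at Day 7, so background cells cannot be separated from the booster response or checked for balance between groups

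*Protocol*

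**What the plan says.** Protocol 2.0 sets the primary objective: "To compare the B memory and plasmablast populations between girls and young women that received either a primary 2 or 3 dose series". Protocol 6.2 then treats the two populations differently.

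- Memory B cells: "The difference between the visit 1 and visit 3 Bmem will be obtained for all subjects".
- Plasmablasts: "Plasmablast numbers and frequencies will be obtained by FACS analysis of the week one samples". No Visit 1 count, background correction or adjustment is described.

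Protocol 4.6.3 gives the assay limit: "Because plasmablasts do not express a BCR, HPV specific PBs cannot be isolated". It accepts this limit on the ground that "it has been estimated that approximately 70% of PBs are antigen specific within a week following vaccination". Memory B cells, by contrast, are sorted with labelled HPV pseudovirus. Bulk sequencing of plasmablasts is planned, but no rule turns it into an HPV-specific count.

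Pre-booster cells exist. Protocol 4.6.1, on the B cell blood, says "Samples will be collected from all participants at visits 1 to 3". The SAP is limited to demographic, clinical and serology data, so it adds nothing on plasmablasts.

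**The concern.** The population that can be sorted by HPV specificity has a baseline, and the one that cannot be sorted has none. By the protocol's own figure, about 30% of the cells counted at one week are not antigen specific. A Day 7 total therefore combines the booster response with whatever was circulating anyway, and nothing in the plan tells the two apart.

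The groups make this matter more. Protocol 3.0 defines them by past schedule and by age at first dose (9-13 years in Groups 1 and 2, 16-26 in Group 3). No randomisation is described for this study, and Protocol 4.2.1 allows recruitment from a provincial programme as well as from the earlier trial. Balance of background across groups cannot be taken for granted, least of all against Group 3. With "This is a 3 arm study with 6 girls per group" (Protocol 3.0), even a chance imbalance could shift the comparison.

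**Working it through.** **Inputs.** From the documents: 6 per group (Protocol 3.0); antigen-specific share about 70% (Protocol 4.6.3). The two-sided 0.05 level is borrowed from the SAP, which states it for changes in antibody over time. The documents give no effect size, SD or power for plasmablasts, so there is no figure of the plan's own to reproduce. True ratios, SDs and correlations below are assumptions.

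**1. Ratio of totals, equal background.** Let *s* be the specific share in the reference group and *R* the true ratio of specific cells, other group over reference. Scale the reference total to 1, so background is 1 − *s* in both groups. The observed ratio is *sR* + (1 − *s*).

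- 70% in the higher group, *R* = 0.5: 0.7 × 0.5 + 0.3 = 0.65, or 1/0.65 = 1.54-fold. Share of the log effect kept: ln 0.65 / ln 0.5 = 0.62, so 38% is lost.
- 70% in the lower group, *R* = 2: 0.7 × 2 + 0.3 = 1.7-fold. Share kept: ln 1.7 / ln 2 = 0.77, so 23% is lost.
- Varying *s* in the higher group: at 50%, 0.5 × 0.5 + 0.5 = 0.75 (1.33-fold); at 90%, 0.9 × 0.5 + 0.1 = 0.55 (1.82-fold).

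**2. 70% in both groups.** Totals are 0.70/0.7 = 1.00 and 0.35/0.7 = 0.50. The ratio is 2-fold, with nothing lost. Background is then no longer equal (0.30 against 0.15); it scales with the response.

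**3. Absolute difference, equal background.** Totals are 1.00 and 0.65, a difference of 0.35. Specific cells are 0.70 and 0.35, also a difference of 0.35. There is no bias, only added variance.

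**4. Unequal background.**

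- Equal specific cells (0.70 in each group) but background 0.30 against 0.45: 1.15 against 1.00, a spurious 1.15-fold difference.
- A true 2-fold difference, with background 0.60 in the lower group and 0.30 in the higher: 0.35 + 0.60 = 0.95 against 0.70 + 0.30 = 1.00. The difference almost disappears.

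The direction depends on which group has more background, and that is not measured.

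**5. What a Visit 1 count does.** Simulation: 20,000 trials per setting, 6 per group, *R* = 0.5, *s* = 0.70, ln SD 0.5 for specific and for background cells, same background distribution at Day 0 and Day 7. Subtracting Day 0 moves the ratio of means from about 0.65 to 0.50. Power of a t-test on the absolute scale:

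| Measure | Power |
|---|---|
| Day 7 only | about 39% |
| Day 7 minus Day 0, background correlation 0 | 32% |
| Day 7 minus Day 0, background correlation 0.5 | 38% |
| Day 7 minus Day 0, background correlation 0.8 | 44% |

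On the log scale, Day 7 totals give about 43%, against 58% if specific cells could be counted directly. Subtraction restores the ratio; it raises power only if background is well correlated within a person.

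**The case against.** The strongest case against is that the protocol discloses the assay limit and gives its reason for accepting it, and that the plasmablast result would be read beside HPV-specific memory B cells and serology, both of which have a baseline. Several further points stand.

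- The 70% is not split by group. A reader might infer that 38% of the log effect is lost at a true 2-fold difference and 46% at 4-fold (0.7 × 0.25 + 0.3 = 0.475; ln 0.475 / ln 0.25 = 0.54). That holds only if the 70% sits in the higher group and background is equal. The first condition implies a share of 0.35/0.65 = 54% in the other group at 2-fold, which no document states. At a common 70% the loss is nil.
- A reader might infer that every comparison is diluted. Protocol 6.2 names no scale for plasmablasts, and an absolute mean difference is not biased under equal background.
- The documents do not say that the non-specific 30% were present before the booster. Non-specific cells that arise after it would survive subtraction.
- The staining panel is not given, so the Visit 1 sort may not already carry plasmablast markers.
- A change score can lower power, as step 5 shows.

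These points limit the size claimed and rule out replacing the Day 7 measure. They do not answer the central one: without a Day 0 count, the assumption of equal background cannot be examined at all.

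**Conclusion.** The point holds as an inexpensive improvement to one of the two parts of the primary objective. As planned, pre-existing plasmablasts cannot be separated from the booster response or compared between groups. On a ratio scale, a true 2-fold difference could appear as about 1.5-fold, 1.7-fold or undiluted, depending on how the 70% applies. On an absolute scale there is no bias if background is equal, and bias of unknown direction if it is not. All of this rests on the protocol's 70% estimate, which the trial does not verify by participant or group, and on assumed true ratios and backgrounds.

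A reader might go further and conclude that the Day 7 endpoint is invalid, or that a null result would necessarily be mistaken for equal memory. The documents support neither: the Day 7 total remains informative, and other baseline-referenced measures are planned beside it.

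**What to change.** In Protocol 6.2:

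- Also count plasmablasts in the Visit 1 PBMC already processed for memory B cells, with the same markers as at Day 7.
- Compare the Day 0 values between the three groups.
- Report the within-person Day 0 to Day 7 rise, or Day 7 with Day 0 taken into account, beside the total Day 7 frequency. Do not demote the Day 7 measure.
- State the analysis scale, since the effect of background depends on it.

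No extra blood or visit is needed. The cost is some use of Visit 1 cells, possibly plasmablast markers added to the Visit 1 stain, and an amendment with REB approval (Protocol 7.1). A low baseline count brings measurement error, so more power is not assured, and subtraction removes only background already present at Day 0. The gain is in interpretation: imbalance becomes visible and can be allowed for.

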7.0 OTHER

7.1 Protocol amendment procedure

No modification of this protocol will be made without formal approval of the local REB.

Documentation of amendments and REB approvals will be maintained with the Essential Documents collection.

7.2 Records retention

Data and study documents will be stored securely for 25 years beyond completion of the study. Destruction will occur in keeping with privacy and confidentiality requirements of the local REB and Standards of Practice at the investigational site at the time. The storage location of study files will be clearly documented.

Appendix 1. Isolation and Freezing of PBMC

Notes: Ficoll 1.077 (Ficoll-Paque Premium GE Healthcare 17-5442-02; 17-5442-03) needs to be at room temperature (RT) and inverted several times before use; Freezing media (50% FBS (heat inactivated):40% RPMI:10% DMSO) once made should be kept on ice; [name] (Sigma Aldrich) should be stored at 4C until use; isopropanol in [name] should be changed every 5 uses; have at least 300ml PBS (sterile/endotoxin free)/subject sample (i.e., 4 ACD tubes) on hand. Always use sterile materials, endo-toxin free where possible, as endo-toxin can cause cell lysis.

Materials needed:

2 x 50ml Ficoll-Paque Premium (1.077 g/ml)
A clean, sterile (autoclaved) 5-inch underlay needle
Autoclave sleeves for underlay needle
1 x 30ml syringe
1 x 10ml syringe
50ml conical tubes
[name]
Nunc cryotubes
One ice bucket with ice
20 ul, 200 ul and 1 ml pipettes
PBS (sterile/endotoxin free)
RPMI
FBS (heat inactivated in 56°C water bath for 1 hour)
Trypan blue
Eppendorfs for cell counting
Hemocytometer
70% ethanol
100% ethanol for cleaning underlay needle
Pen for notes

- Remove 2 x 50 ml Ficoll-Paque tubes from refrigerator and place in 37C bead bath, (typically *before* you go pick up sample from reception) or use unopened Ficoll-Paque at room temperature
- Spray down hood and equipment (i.e., pipettes, filter pipette tip boxes, media bottles) with 70% ethanol and wipe clean with paper towels.
- Set up 6 x 50 ml conical tubes in hood
- Make sure 4 yellow caps (ACD BD Vacutainer tubes) have been mixed (i.e., there is not separation at the top indicating that tubes have not been inverted 8 times, as recommended by BD).
- Remove yellow caps and set aside (do not discard)
- Pipette 10 ml blood into each of 4 x 50 ml conical tubes using a 10 ml stripette
- Consolidate any remaining blood in each glass tube to one tube.
- If there is sufficient blood remaining (i.e., after setting aside 2 ml for plasma), divide extra blood equally into four 50 ml conical vials (typically 4 ml extra blood remains after setting aside 2 ml for plasma, so an additional 1 ml can be added to each 50 ml conical vial).
- Re-cap tube with 2 ml blood for plasma and an additional empty glass tube.
- Centrifuge these two tubes 900xg, 10 min, 25C (with brake)
- Add 2 parts PBS to 1 part blood in each 50 ml conical vial (e.g., if there is now 16 ml blood in each vial, add 32 ml PBS to each tube)
- Invert 50 ml conical tubes and then distribute 1 part PBS/blood mixture from each 50 ml conical equally to two clean 50 ml conical vials (i.e., 16 ml each from two conical vials into a clean conical vial and then repeat).
- Each of the 6 x 50 ml conical vials should now have 32 ml PBS/blood mixture.
- Remove 2 x 50 ml Ficoll-Paque tubes from 37C bead bath, spray down with 70% ethanol and wipe clean with paper towels.

- Invert Ficoll-Paque tubes multiple times, then underlay 15 ml Ficoll-Paque using **underlay** needle and 30 ml syringe to each of 6 x 50 ml conical vials with PBS/blood mixture – **ADD FICOLL-PAQUE VERY SLOWLY AT START** to allow a good gradient to form – you should see a clearly delineated interface between the Ficoll and PBS/blood mixture.
 - o Always underlay 15 ml Ficoll-Paque for each 30-35 ml PBS/blood mixture. If there is less blood total, adjust number of conical vials accordingly or add more PBS to PBS/blood mixture to total 30 ml **BEFORE** underlaying Ficoll-Paque. There can be as much as 3 parts PBS to 1 part blood, though 2 parts PBS to 1 part blood is preferred.
 - o When underlaying with Ficoll-Paque, the very slow initial rate should be ~2 seconds per ml. After underlaying first 15ml of Ficoll-Paque in conical tube, remove needle and place at the bottom of next conical tube and start again. DO NOT expel last bit of Ficoll-Paque from 30 ml syringe, as bubbles will disturb gradient.
- Once centrifuge has stopped, remove plasma sample and empty glass tube from centrifuge and place 6 x 50 ml conical vials with PBS/blood mixture into centrifuge
- Centrifuge 6 x 50 ml conical vials 400xg for 35 min NO BRAKE at 18°C
- Remove 105 ul plasma from glass tube to a cyrotube and then remaining plasma into a separate cyrotube
- Label 105 ul plasma sample with 1. Subject ID, 2. Date, 3. Sample contents (i.e., ‘plasma’). Mark cap with a dot.
- Label additional plasma sample with 1. Subject ID, 2. Date, 3. ‘plasma’, 4. Study group (e.g., ‘Exp’ for *HPV-Exposed group*), 5. Time point (e.g., ‘M6’ for month 6).
- Store 105 ul sample in ‘[name]’ box at -70C and additional plasma sample in ‘Plasma box #N’ at -70C.
- Once spin has stopped, remove lymphocytes (white, cloudy, ‘buffy coat’) at interface to 2 x 50 ml conical tubes with sterile 1 ml filter pipette
- You should have approximately 20-25 ml/conical when no more lymphocytes are visible
- Add PBS to each 50 ml conical vial containing isolated PBMC up to 50 ml and invert 1-2 times
- Centrifuge 300xg for 10 min NO BRAKE at 20°C
- During spin, prepare 2 x eppendorf tubes for counting (100 ul trypan blue, 50 ul PBS each)
- After removing conical vials from centrifuge, spray down with 70% ethanol and wipe clean with paper towels.
- Gently decant off supernatant and dislodge pellets by tapping on hood. (N.b., from this point forward, keep cells on ice when not manipulating.)
- Resuspend each pellet in 1 ml PBS. Then add 19 ml PBS to one conical vial, invert, and transfer over cells/PBS to 2nd vial. Then add a second 19 ml PBS wash to 1st vial, invert, and transfer over wash to 2nd vial. Use a 1 ml pipette to collect any remaining wash from 1st vial and transfer to 2nd vial. Now there should be 40 ml cells/PBS in 1 x 50 ml conical vial. If < 60 ml blood contributed to PBMC isolation, adjust accordingly: **1 ml PBS/ 1.5 ml blood** (e.g., 40 ml PBS/60 ml blood)
- Cool down centrifuge by changing temperature from 20°C to 4°C
- Invert conical of cells before taking out 50 ul for counting to ensure homogeneity
- Add 50 ul cells to 1 eppendorf tube with trypan blue/PBS, vortex briefly, and count 10 ul of this sample. Repeat dilution and count for accuracy (adding cells immediately before counting each tube). Dilution factor is 4.
- Calculate how many million cells total (e.g., 2.5×10^6 cells/ml x 40 ml = 100×10^6 cells). Figure out how many cryotubes to freeze cells with. Freeze 1 tube with 10×10^6 cells/ml freezing media; and ≥ 3 tubes with 10×10^6 - 40×10^6 cells/ml freezing media/tube.
- When aliquoting cells in freezing media (f.m.) into cryotubes, where there will be:
 -
 - 1.0×10^7 cells **1.0-4.0x10⁷ cells** $1.0-4.0 \times 10^7$ cells $1.0-4.0 \times 10^7$ cells ...
 - 1 ml f.m. | 1 ml f.m. 1 ml f.m. 1 ml f.m.
 - 1 tube 1 tube 1 tube 1 tube
 -
 - if there are any remaining cells in freezing media in the multi-aliquot conical vial (and there probably will be a couple of hundred microliters), then add to one of the $1.0-4.0 \times 10^7$ cell tubes.
 - Centrifuge 50 ml conical tubes (one with 10×10^6 cells and the other with remaining cells) at 300xg, 5 min, 4°C (with brake)

- During spin, make freezing media using 5 parts FBS: 4 parts RPMI: 1 part DMSO in excess of total # of cryotubes, assuming 1 ml freezing media per cryotubes (e.g., if there will be 4 cryotubes total, make 5 ml freezing media). Vortex to mix freezing media and then place on ice.
- Prepare cryotubes for cells with the following label: 1. Subject ID, 2. Date, 3. $nx10^7$ PBMC, 4. Study group, 5. Time point
- After removing conical vials from centrifuge, spray down with 70% ethanol and wipe clean with paper towels.
- Gently decant off supernatant and dislodge pellets by tapping on hood. (Keep cells on ice when not manipulating.)
- Bring up cells in appropriate amount of freezing media (1 ml freezing media/cryotube). Add freezing media to multi-aliquot conical ml by ml, washing sides of conical as freezing media is expelled.
- Pipet cells up/down gently before removing each ml to a cryotube (this ensures even cell density). Transfer each cryotube to [name] after adding cells.
- Transfer [name] to -80°C and leave at least overnight.
- Spray down outside of underlay needle with 70% ethanol and rinse 4 times with 100% ethanol using a 10 ml syringe before placing in autoclave sleeve.
- Autoclave underlay needle before using again – or use disposable, sterile, endotoxin free underlay needles.
- Can remove cells from [name] and store in -80°C freezer until shipping to [name] Lab – BUT DO **NOT** STORE IN LIQUID NITROGEN VAPOR UNDER ANY CIRCUMSTANCES!
- Please ship to [name] Lab on dry ice

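### Appendix 1 calls for the study group on PBMC and larger plasma tubes; if the dose group is written there, the laboratory could see it while gating cells for the primary objective

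*Protocol*

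**What the plan says.** Three places in the protocol deal with labels.

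- Section 4.6.1, on the collection tubes: "Each tube of blood will be clearly labeled with PID and visit number, secondary identifier (SID) and date and time of collection".
- Section 4.6.2, on PBMC: "PBMC should be labeled by PID and in sequence per participant". The same section says that PBMC are "stored and shipped as per the lab manual of Appendix 1".
- Appendix 1, on the frozen aliquots. The PBMC cryotube carries subject ID, date and cell number, and then "PBMC, 4. Study group, 5. Time point". The additional plasma tube also has the field "4. Study group (e.g"; the example there is an abbreviation for an HPV-exposed group. The 105 ul plasma tube has no group field.

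PBMC and plasma go to the laboratory in Seattle. The primary objective is "To compare the B memory and plasmablast populations between girls and young women that received either a primary 2 or 3 dose series", and section 6.2 takes both cell populations from these samples. Section 5.3 keeps personal identifiers off the tubes but is silent on group. Section 6.1 provides for de-identified data to go to the Seattle laboratory, without naming the variables or the timing. Neither document describes masking of the laboratory.

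**The concern.** Counting cells by flow cytometry involves judgement about where gates are set. The protocol gives no gating rule. For memory B cells, section 4.6.3 describes binding to labelled pseudovirus and then says "That together with phenotypic markers allows us to isolate HPV-specific Bmem by FACS". For plasmablasts it says that HPV-specific cells cannot be isolated, so antigen binding cannot anchor that count.

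An operator who can read the dose group on the tube could be influenced by it, even without intent, and a later reader could not rule this out. With six participants per group, each person is one sixth of a group mean, so a few altered gates could shift a comparison. The choice of cells to clone is also open to influence. It feeds the secondary objective, which begins "To compare the extent of somatic hypermutation and the variable gene usage between girls".

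**Working it through.** The documents give no figure to reproduce. The check sets the label instructions side by side and then traces the samples.

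**1. Label contents**

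| Tube | Where specified | Group listed? |
|---|---|---|
| Blood collection tube | Section 4.6.1 | No |
| PBMC | Section 4.6.2 | No |
| PBMC cryotube | Appendix 1 | Yes |
| Additional plasma tube | Appendix 1 | Yes |
| 105 ul plasma tube | Appendix 1 | No |

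Sections 4.6.1 and 4.6.2 neither list the group nor forbid it. Because 4.6.2 hands processing, storage and shipping to Appendix 1, the appendix is operative text.

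**2. What the field would contain**

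Appendix 1's examples are an HPV-exposed group and a month-6 time point. This trial has three groups defined by dose number and age (section 3.0) and visits at days 0, 7 and 30 (section 3.3), so the examples do not fit. Site staff told to write a study group could naturally write the group from section 3.0, but the text does not settle this.

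**3. Who would see it**

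Section 4.6.2 sends PBMC to Seattle, 4.6.3 and 6.2 describe the sorting and counting, and 6.1 sends data to that laboratory. Together these imply that Seattle does the cytometry. No sentence says so outright.

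**4. How many samples**

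- Participants (section 3.0): 3 groups x 6 = 18.
- B-cell blood is drawn at visits 1 to 3 (section 4.6.1): 18 x 3 = 54 planned PBMC samples.
- By use in section 6.2: memory B cells at visits 1 and 3, 18 x 2 = 36 samples; plasmablasts at visit 2, 18 x 1 = 18 samples; 36 + 18 = 54.

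These are samples, not readings: section 6.2 speaks of type-specific memory B cells, so one sample may give several readings. The number obtained may be below 54, since section 4.8.2 allows retention of a participant with no visit 2 blood.

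**5. Would relabelling alone be enough?**

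Section 5.0 collects birth month and year and the month and year of each HPV dose. If those items were among the data sent under 6.1:

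- Group 1 has 2 dose dates; Groups 2 and 3 have 3.
- Age at first dose is 9-13 in Groups 1 and 2 (under 14) and 16-26 in Group 3 (16 or more). The gap is at least 16 - 14 = 2 years, so dates to the month are precise enough.

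The two items together separate all three groups. Section 6.1 does not say whether they are sent or withheld.

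**6. What is not reached**

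The SAP's co-primary endpoints (cLIA) and co-secondary endpoints (total IgG) are measured by Merck on serum, which is shipped separately. The Appendix 1 labels do not go on those tubes.

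**The case against.** The strongest reply has four parts.

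- *The lists do not conflict.* Section 4.6.1 concerns collection tubes, and 4.6.2 defers to the appendix and is plainly not exhaustive, since it omits the date. This stands: the lists can be read as cumulative. It does not remove the concern, because on that reading the group does go on the tubes shipped to Seattle.
- *Appendix 1 is a generic manual that was not adapted.* This is plausible given its examples. It makes the content of the field uncertain, which is a reason to define or remove it.
- *No promise is broken.* This is correct. Groups are defined by past vaccination and neither document claims masking. A reader might infer that a blinding rule has been violated, or that the laboratory did know the groups and the cell counts are biased. The documents support neither: there is no such rule, the field's content is unknown, and Seattle's role in gating is an inference.
- *Much of the work does not depend on the operator.* This stands in part. Somatic hypermutation is found by comparing sequences with germline databases, and memory B cells are identified by pseudovirus binding as well as phenotype. Visible group could affect which cells are picked, but not the sequence comparison. The concern is strongest for plasmablasts.

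**Conclusion.** The point holds as a gap worth closing. Following Appendix 1 as written could expose the dose group on all 54 planned PBMC samples during the gating and cell selection that serve the protocol's primary objective and its hypermutation and V-gene objective. This rests on two assumptions that the documents leave open: that the field would hold the dose group, and that the Seattle laboratory does the cytometry. The documents give no basis for estimating the direction or size of any bias. The SAP's cLIA and total IgG endpoints are not affected. A reader might also infer from section 6.1 that dose and birth dates are sent to the laboratory; the text does not say so, and the point there is only that it does not exclude them.

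**What to change.** 1. In Appendix 1, delete the study group from the PBMC cryotube and additional plasma tube labels, or replace it with a non-revealing code. Use PID plus visit code, in line with section 4.6.1. Group is not needed for traceability, since PID and visit identify the sample.
2. In section 6.1, state that group, number and dates of Q-HPV doses, and birth date or age are withheld from the Seattle laboratory until gating, cell counts and cell selection are locked.

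The cost is two label edits and a few sentences; no visit, sample or assay changes. The clinical site must hold the group key, a lock step must be defined, and the laboratory receives the group and dose history later.
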